6.3 PATIENT SETS ANALYSED

- **Randomised set (RS):**
This patient set includes all randomised patients, whether treated or not.
- **Treated set (TS):**
This patient set includes all patients who were dispensed study medication and were documented to have taken at least one dose of investigational treatment.
- **Full analysis set (FAS):**
This patient set includes all patients randomised in the TS who have a baseline and at least one on-treatment HbA_{1c} value.
- **FAS-completers-24 (FASC24):**
This patient set includes all patients in the FAS who complete a minimum treatment duration of 149 days, did not prematurely discontinue the trial and have an available HbA_{1c} measurement within the time window for the Week 24 visit (Visit 98 for non-Japanese and Visit 7 for Japanese patients up to day 176). This analysis set is not required for the analysis at Week 52. See [Table 6.7: 1](#).
- **Per protocol set (PPS):**
This patient set includes all patients in the FAS who do not have any IPVs relating to efficacy, cf. [Table 6.2: 1](#).

Table 6.3: 1 Patient sets analysed

Class of endpoint	Patient set			
	TS	FAS	PPS	FASC24
Primary endpoint		Primary analysis	Sensitivity analysis	Sensitivity analysis
Secondary and further endpoints		X		
Safety endpoints	X			
Demographics	X			
Baseline efficacy variables		X		

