**A total of 300 patients will be randomised.**

Proprietary confidential information.

© 2015 Boehringer Ingelheim International GmbH or one or more of its affiliated companies. All rights reserved.

This document may not - in full or in part - be passed on, reproduced, published or otherwise used without prior written permission.

Based on pooled data from the 1218.36 and 1218.63 trials [REDACTED] assuming a standard deviation of 1.2% in both groups in the FAS with a 0.77% difference in HbA1c change from baseline in treatments, a number of 150 patients in each treatment arm will show superiority with a power >99%. This determination of power is based on a Student's t-test and a two-sided significance level of 5%.

Software package nQuery version 7.0 was used to derive the sample size.

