Baseline values will not be carried forward in general, but can be used for interpolation. Only for patients with rescue medication before the first on-treatment HbA_{1c} measurement, baseline HbA_{1c} values will be used to replace values after the start of rescue medication.

Missing values within a course of measurements on treatment will be interpolated based on the last observed value before the missing visit and the first observed value after the missing visit. This is independent from the selection of a value as the picked visit value (cf. [Section 6.7](#)) to be used in the descriptive analysis by visit. Replacement of missing values will only be performed for visits up to the planned visit to be reached by all randomised patients in the trial.

Interpolation will be done according to the formula described below:

Let: D_0 = date of a visit with a missing endpoint value;

D_1 = date of the next-visit (with end-point value non-missing) after the visit with missing endpoint;

D_{-1} = date of a previous-visit (with end-point value non-missing) before the visit with missing endpoint;

E_i = endpoint value for visits D_i for $i = -1, 0, 1$.

Then the missing endpoint value can be interpolated as:

$$E_0 = E_{-1} + \left((E_1 - E_{-1}) \times \frac{D_0 - D_{-1}}{D_1 - D_{-1}} \right).$$

Multiple imputation (MI)

A multiple imputation approach will be used as a sensitivity analysis for the primary endpoint. Further details can be found in [Section 7.4.2](#).

Non-completers considered failure (NCF)

For binary endpoints like a treat to target response of $HbA_{1c} < 7.0\%$ a conservative method to replace missing values is to consider them as “failures”. Missing data due to early discontinuation will be replaced as “failure” (e.g. $HbA_{1c} \geq 7.0\%$) up to the planned final visit to be reached by all patients. Similarly, values obtained after the start of rescue therapy will be considered “failure”.

For binary endpoints that are derived from quantitative endpoints (e.g. HbA_{1c}), missing values within a course of measurements on treatment will be replaced on the basis of the corresponding imputed value of the underlying quantitative endpoint (e.g. based on imputation as described for HbA_{1c}).

Table 6.6: 1 Summary of imputation methods for efficacy endpoints

Imputation method	Endpoint	Handling of missing values	Handling of values after rescue therapy

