Repeated and unscheduled efficacy measurements will be assigned to the nominal visits and listed in the subject data listings according to the time windows described above. Only one observation per time window (visit value / picked value) will be selected for analysis at an on-treatment visit – the value will be selected which is closest to the protocol planned visit day; except for last study drug intake. In case of last study drug intake, the value which is closest to the date of last study drug intake is chosen. If there are two observations which have the same difference in days to the planned day or if there are two observations on the same day, the earliest value will be used. If an observation is available on the last day of treatment, this observation will be preferably selected over any later observation that is still within the time window. If there are multiple values within the time window of the last visit,

including a value on the last day of drug intake, the value on the last day of drug intake is used as the value of the last visit.

Note: For LOCF imputation, the last observed on-treatment value will be carried forward, whether or not it was selected in the previous time window. Also for interpolation any valid values can be used, regardless of whether they were selected as visit values. For more details on LOCF refer to [Section 6.6](#).

For daily basal insulin the value at the visit will be determined as the last prescribed dose prior to the picked HbA1c value of the visit.

Visit windows will not be applied to hypoglycaemia or use of rescue therapy and events will not be assigned to visits. All on-treatment events will be considered in the analysis.

Visit windows for safety variables

Safety measurements will be assigned to the nominal visit as recorded on the eCRF or as provided by the laboratory. In general, visit windows will not be applied. However, for the Week 24 analysis, if a Japanese patient stops drug intake prior or at day 175 a residual period of 7 days will be added for safety analysis. If a Japanese patient does not stop drug intake prior day 176, no residual period is added for safety analysis at Week 24.

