7.5.2 Secondary endpoints

Proportion of patients with at least one hypoglycaemia accompanied by a glucose value during 24 weeks of treatment

Logistic regression for the proportion of patients experiencing at least one hypoglycaemia after 24 weeks will be performed on the FAS (OC); all on-treatment hypoglycaemias will be considered:

- up to drug stop date if a patient prematurely discontinues (Japanese patients that prematurely discontinue prior or at day 175)

- up to trial medication stop date – 1 if a non-Japanese patient does not prematurely discontinue
- up to day 175 if a Japanese patient does not prematurely discontinue prior day 176.

The model will include *treatment* as fixed effect and *baseline HbA_{1c}* and *baseline daily basal insulin dose* as linear covariates.

Frequencies regarding the number and percentage of patients experiencing at least one hypoglycaemia accompanied by a glucose value during 24 weeks in each treatment group will also be presented based on FAS(OC) .

Proportion of patients with HbA_{1c} on treatment <8.0% after 24 weeks of treatment

Logistic regression for the patients achieving HbA_{1c} <8.0% at Week 24 will be performed on FAS (NCF); patients who do not complete 24 weeks of treatment will be considered non-responders. The model will include *treatment* as fixed effect and *baseline HbA_{1c}* and *baseline daily basal insulin dose* as linear covariates. Patients with baseline HbA_{1c} <8.0% will be excluded from the analysis.

A frequency table with the number and percentage of patients with HbA_{1c} <8.0% at Week 24 in each treatment group will be also be presented based on FAS (NCF).

Proportion of patients with HbA_{1c} on treatment <7.0% after 24 weeks of treatment

Logistic regression for the patients achieving HbA_{1c} <7.0% at Week 24 will be performed on FAS (NCF); patients who do not complete 24 weeks of treatment will be considered non-responders. The model will include *treatment* as fixed effect and *baseline HbA_{1c}* and *baseline daily basal insulin dose* as linear covariates. Patients with baseline HbA_{1c} <7.0% will be excluded from the analysis.

Frequencies regarding the number and percentage of patients with HbA_{1c} <7.0% at Week 24 in each treatment group will be also be presented based on FAS (NCF).

Proportion of patients with HbA_{1c} lowering by at least 0.5% after 24 weeks of treatment

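### The FASC24 discontinuation clause and the later value used for interpolation have no Day 176 limit for Japanese patients, so post-Week 24 information can enter secondary Week 24 HbA1c analyses (not the primary one)

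*SAP*

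**What the plan says.** SAP 6.3 sets three joint conditions for FASC24. The patient must have enough treatment days and must not have left early ("who complete a minimum treatment duration of 149 days, did not prematurely discontinue the trial"), and must have an HbA1c in the Week 24 window. For Japan that window is Visit 7, capped at Day 176; Table 6.7: 1 gives Days 149 to 176. Table 6.3: 1 names FASC24 as a sensitivity analysis of the primary endpoint, and SAP 6.3 adds that the set is not needed at Week 52.

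SAP 6.6 covers gaps in the HbA1c series: "Missing values within a course of measurements on treatment will be interpolated based on the last observed value before the missing visit" and the first one observed after it. Only visits planned for all randomised patients may be filled. SAP 6.7 lets any valid value serve for interpolation, whether or not it was picked as a visit value. Table 6.6: 1 applies interpolation to LOCF and, through the underlying HbA1c, to the responder endpoints analysed under NCF.

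Elsewhere the SAP does separate Week 24 from later follow-up in Japan. Under 6.2, efficacy violations from Day 176 onwards do not exclude a patient from analysis sets. Under 7.5.2, hypoglycaemia is counted "up to day 175 if a Japanese patient does not prematurely discontinue prior day 176". Under 7.8, adverse events are cut at Day 175.

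**The concern.** A Week 24 analysis should depend only on what happened up to Week 24. Two rules allow otherwise, and in one country only.

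First, SAP 6.2 places the end of the trial in Japan at Week 52, so a condition about leaving the trial early, with no day attached, reaches past Week 24 there. Such removals need not be random: SAP 6.6 itself expects patients with lack of efficacy to drop out more often. A set meant to test the robustness of the primary result would then be selected on a later outcome.

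Second, a missing Week 24 value is handled differently by country. A Japanese patient may have a later on-treatment value to interpolate towards; a non-Japanese patient cannot.

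Both results would also depend on how much post-Day 176 follow-up from Japan is in the database at the Week 24 lock, which SAP 7.8 separates from the 52-week analysis. At stake are one named sensitivity analysis, the LOCF summaries and three secondary endpoints.

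**Working it through.** **1. The rules side by side**

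| SAP rule | Limit for Japan at Week 24 |
|---|---|
| 6.2, violations | Day 176 |
| 6.3, FASC24 HbA1c window | Day 176 |
| 6.3, FASC24 discontinuation clause | none |
| 6.6, visit that may be filled | visits planned for all patients |
| 6.6 and 6.7, later value used to fill it | none |
| 7.5.2, hypoglycaemia | Day 175 |
| 7.8, adverse events | Day 175 |

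The Day 176 cap in FASC24 qualifies the measurement. It does not qualify the separate condition on discontinuation.

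**2. Why only Japan is exposed.** For non-Japanese patients the Week 24 HbA1c window runs from Day 149 to 7 days after the last dose (Table 6.7: 1 and SAP 6.7). Any on-treatment value after Day 149 therefore falls inside the window, and none can lie beyond it. For Japan the window closes at Day 176 while treatment goes on.

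**3. The plan's own figure.** Protocol 7.6 proceeds by "assuming a standard deviation of 1.2% in both groups in the FAS" and a difference of 0.77%, and says "a number of 150 patients in each treatment arm will show superiority with a power >99" percent.
- Noncentrality = 0.77 / (1.2 × √(2/150)) = 5.56.
- A two-sided 5% t-test gives power of 99.98%, so the stated figure is reproduced.

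**4. Size for FASC24.** Japan is to contribute 100 of 300 patients (Protocol 3.3). The documents give no dropout rate, so these are assumptions: 90 Japanese patients and 270 patients in all reach Week 24 with a value, and 3% to 15% of the 90 stop between Day 176 and Week 52.
- 90 × 0.03 = 2.7 and 90 × 0.15 = 13.5, so about 3 to 14 patients.
- 2.7/270 = 1.0% and 13.5/270 = 5.0% of the set.

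A harsher assumption is 30% of all 100 Japanese patients, or 30 removed. That leaves 135 per arm if losses are even:
- power 99.95%;
- 95% half-width 1.96 × 1.2 × √(2/135) = 0.29, against 0.27 with 150 per arm.

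The issue is selection, not precision.

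**5. Size for interpolation.** SAP 6.6 gives E0 = E-1 + (E1 − E-1) × (D0 − D-1)/(D1 − D-1). Take Week 18 (Day 127) as the earlier visit and Week 24 (Day 169) as the missing one. The weight on the later value is then 42/(D1 − 127). The HbA1c schedule in Japan after Week 24 is not given, so the later visits are assumptions:
- Week 30 (Day 211): 42/84 = 0.50
- Week 36 (Day 253): 42/126 = 0.33
- Week 52 (Day 365): 42/238 = 0.18

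Example: Week 18 is 8.2%, Week 24 is missing and Week 36 is 7.4%. Interpolation gives 8.2 − 0.8 × 0.333 = 7.93%, a responder for <8.0% if baseline was at least 8.0%. Without a value after Day 176, LOCF would carry 8.2% forward, which is above the target.

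If 1% to 3% of 90 Japanese patients have such a gap, 1 to 3 are affected. In the extreme case where all fall in one arm of 150 and all change status, the proportion moves by 1/150 = 0.7 to 3/150 = 2.0 percentage points. At 10% of 100 patients it would be 10/150 = 6.7 points. The target analyses exclude patients already below the target at baseline, so numerator and denominator are both smaller there.

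**6. Primary analysis.** SAP 7.4.1 uses FAS (OC) with week levels up to Week 24, and SAP 6.6 replaces nothing under OC. Neither rule enters it.

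**The case against.** The best reply is that the intent can be recovered. Protocol 7.3 defines completers by 24 weeks of treatment and an HbA1c value at that point, with no later condition. The visible rows of SAP Section 4 announce no change to this, and the set exists only for Week 24. A programmer who knew all this would probably not drop a patient who stopped at Week 40. That supports the correction rather than removing the need for it: the literal clause gives a different set, and the SAP is what gets programmed.

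A second reply is that SAP 7.8 bases its analysis on data up to 24 weeks at database lock. If that cut also applied to efficacy, it would close the interpolation gap, but it stands in the safety section. Sections 5.3 and 7.4.2, among others, are wholly or partly redacted and may hold a limit; the point concerns the visible text only.

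Third, both rules apply equally to the two arms, and no direction of bias can be shown. This stands.

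A reader might also infer more than the documents support:
- *That FASC24 has no Day 176 limit at all.* It has one, on the HbA1c window.
- *That a third of the sample is changed.* One third (100/300) is the share subject to the rules. Only late stoppers, or patients lacking a Week 24 value but having a later one, are changed.
- *That rescue use is also uncapped in Japan.* SAP 6.7 says "Visit windows will not be applied to hypoglycaemia or use of rescue therapy and events will not be assigned to visits". But that sentence covers hypoglycaemia too, whose cut-off is set separately in 7.5.2, so it does not show that a cut-off for rescue is absent. Rescue use is not a visible primary or secondary endpoint, and the further-endpoint text is redacted. Rescue begun after Day 176 cannot alter earlier HbA1c values, since only values after rescue are set to missing.

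**Conclusion.** The point holds in a narrow form. As written, two Week 24 rules depend on events or values after Day 176 in Japan, contrary to the protocol's completer definition and to the limits the SAP applies elsewhere. The primary MMRM and its power are untouched.

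The numbers are small: about 3 to 14 patients for FASC24 and perhaps 1 to 3 for interpolation. They rest on assumed rates of completion, late stopping and missed visits. They also assume that the later follow-up is in the database at the Week 24 lock; if it is only partly there, fewer patients are affected. The correction is still worth making before lock, because it removes a country-dependent rule from a named sensitivity analysis and three secondary endpoints.

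**What to change.** - **SAP 6.3, FASC24:** replace the open clause with a dated one, for example: *had not stopped trial medication early before the Week 24 visit (Japan: before Day 176)*.
- **SAP 6.6 and 6.7, interpolation:** add that for all Week 24 analyses only HbA1c values up to Day 176 may be used to fill a gap. A Japanese patient without a Week 24 value then falls under the same LOCF and NCF rules as any other patient.

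While editing, state how NCF treats a patient who stayed on treatment but has no Week 24 value. Table 6.6: 1 covers gaps after premature discontinuation and gaps with a later value, but not this case, which the second change makes possible in Japan as well.

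The cost is two phrases and one clarifying sentence in the SAP. No new data are needed, and the primary analysis does not change.

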6.5 POOLING OF CENTRES

This section is not applicable as no analysis by centre will be performed.

6.6 HANDLING OF MISSING DATA AND OUTLIERS

Patients may drop out of the trial before they reach the planned observation time. In particular, patients with a lack of efficacy can be expected to drop out with a higher probability than patients showing a good response. Therefore various methods will be used to assess the

impact of missing data on the efficacy endpoints of the trial. The following paragraphs give a general description of the various approaches.

Original Results (OR) analysis

For some of the efficacy endpoints, analysis will be done directly on the observed data, without any derivation performed on them. OR analysis is relevant in cases rescue therapy was taken.

Observed cases (OC)

One general approach that is possible for all endpoints is to analyse only the available data that were observed while patients were on treatment, i.e. excluding the missing data. Missing data in this analysis will not be replaced.

For all efficacy endpoints using OC, this OC-technique will be adapted by setting any values taken after rescue medication to missing. In addition values after the addition of a new anti-diabetic therapy or an increase in metformin and/or AGI dose as specified in [Section 5.3](#) will be set to missing.

It should be noted that this method provides unbiased estimates only under the assumption that the data are missing at random; and so, this method is likely to lead to non-conservative estimates of the treatment effects in case of data missing due to patients dropping – out because of lack of efficacy of the study medication under treatment.

Observed cases – Rescue observed cases (OC-ROC)

In this case, values taken after rescue medication are neither set to missing nor are imputed otherwise but taken as measured.

Last observation carried forward (LOCF)

An alternative method for quantitative endpoints is to replace missing values due to early discontinuation of a patient by her/his last observed measurement on treatment. This method tends to result in more conservative estimates than an OC-analysis.

The last observation on-treatment must not necessarily be a value selected as a visit value as described in [Section 6.7](#). If multiple measurements were performed within a time window for a visit, the last on-treatment value within the time window will be carried forward, while the visit value can be the value that was observed closest to date of last drug administration or the first value observed in the time window.

Baseline values will not be carried forward in general, but can be used for interpolation. Only for patients with rescue medication before the first on-treatment HbA_{1c} measurement, baseline HbA_{1c} values will be used to replace values after the start of rescue medication.

Missing values within a course of measurements on treatment will be interpolated based on the last observed value before the missing visit and the first observed value after the missing visit. This is independent from the selection of a value as the picked visit value (cf. [Section 6.7](#)) to be used in the descriptive analysis by visit. Replacement of missing values will only be performed for visits up to the planned visit to be reached by all randomised patients in the trial.

Interpolation will be done according to the formula described below:

Let: D_0 = date of a visit with a missing endpoint value;

D_1 = date of the next-visit (with end-point value non-missing) after the visit with missing endpoint;

D_{-1} = date of a previous-visit (with end-point value non-missing) before the visit with missing endpoint;

E_i = endpoint value for visits D_i for $i = -1, 0, 1$.

Then the missing endpoint value can be interpolated as:

$$E_0 = E_{-1} + \left((E_1 - E_{-1}) \times \frac{D_0 - D_{-1}}{D_1 - D_{-1}} \right).$$

Multiple imputation (MI)

A multiple imputation approach will be used as a sensitivity analysis for the primary endpoint. Further details can be found in [Section 7.4.2](#).

Non-completers considered failure (NCF)

For binary endpoints like a treat to target response of $HbA_{1c} < 7.0\%$ a conservative method to replace missing values is to consider them as “failures”. Missing data due to early discontinuation will be replaced as “failure” (e.g. $HbA_{1c} \geq 7.0\%$) up to the planned final visit to be reached by all patients. Similarly, values obtained after the start of rescue therapy will be considered “failure”.

For binary endpoints that are derived from quantitative endpoints (e.g. HbA_{1c}), missing values within a course of measurements on treatment will be replaced on the basis of the corresponding imputed value of the underlying quantitative endpoint (e.g. based on imputation as described for HbA_{1c}).

Table 6.6: 1 Summary of imputation methods for efficacy endpoints

Imputation method	Endpoint	Handling of missing values	Handling of values after rescue therapy
OR	Continuous, binary, time to event and count	No imputation	All data included as measured. Multiple measurements per visit possible.
OC	Continuous	No imputation	Excluded – considered missing. One picked value per visit (cf. Section 6.7).
OC-ROC	Continuous, binary, time to event and count	No imputation	Included as measured. One picked value per visit (cf. Section 6.7).
LOCF	HbA _{1c} (at each visit and change from baseline)	Missing values at the end of the trial are replaced by the last on-treatment value. Missing values with subsequent present on-treatment values are imputed by interpolation. Baseline values are not carried forward, except where rescue medication is taken prior to first on-treatment measurement. Baseline values can be used in interpolation.	Values after the start of rescue therapy are replaced by the last available measurement. If no on-treatment HbA _{1c} measurement prior to rescue therapy is available baseline values are carried forward.
MI	HbA _{1c}	Missing values are imputed by a two-step approach. Firstly, a monotone missing pattern is generated in the data (MCMC method). Secondly, missing values are imputed by a sequential regression based method.	Considered missing and thus imputed.

Table 6.6: 1 Summary of imputation methods for efficacy endpoints (cont.)

Imputation method	Endpoint	Handling of missing values	Handling of values after rescue therapy
NCF	Binary endpoints derived from continuous endpoints (e.g. HbA _{1c} <7.0%)	Missing values after premature discontinuation of trial medication are considered failure (endpoint not achieved). Missing values with subsequent present on-treatment values will be imputed based on the interpolated values for the underlying continuous endpoint.	Values after the start of rescue therapy are imputed as failure.

[REDACTED]

[REDACTED]

Safety and other variables

Missing safety data will not be replaced, but an analysis of the changes from baseline to the last available value under treatment and the minimum and maximum post baseline will be determined for quantitative safety laboratory variables. For safety analysis, as last on-treatment value the last measurement between the first intake of randomised trial drug and drug-stop date + 7 days will be analysed as the last value on-treatment for non-Japanese patients. If a Japanese patient stops drug intake prior or at day 175 a residual period of 7 days will be added for Week 24 safety analysis. If a Japanese patient does not stop drug intake prior day 176, no residual period is added for safety analysis.

Missing dates and times

Missing or partial date and time information for adverse events (AEs) will be replaced according to general Boehringer Ingelheim (BI) rules (cf. [1](#)).

If the date of first drug administration is missing but the patient was randomised and treated, the date of the first drug administration will be set to the date of randomisation.

If the date of first administration is partially missing with the month and year present, the day will be set to the date of randomisation if randomisation was in the same month. If randomisation was in the month prior to the first drug administration the missing day will be imputed as the first day of the month.

A missing time of first drug administration will be imputed as 12:00 o'clock noon, missing administration times at on-treatment visits will be imputed by 8:00 o'clock in the morning.

As a general rule, a missing drug stop date will be imputed according to the following principles:

- If an End of Treatment (EoT) visit is documented, it should be the date of the EoT visit (Visit 98).
- If the date is incomplete with only month and year and the EoT visit is missing, it should be the first day of the following month.
- If the patient is lost to follow-up it should be the date of the last visit + the longest treatment duration based on drug supply + 1 day.
- All other cases need to be assessed by the trial team on an individual basis, trying to use the points above as guidance.
- After application of any of the first 3 rules, the post-treatment phase starts at the same day as the imputed drug stop date (instead of treatment stop + 1 day).

If only the year of birth is known, the day and month of birth will be imputed as 01 January. If month and year are known, the day of the birth will be imputed as 01.

For other incomplete date information always the midpoint of the possible interval will be used. If only the year is present the day and month will be imputed as 01 July, if year and month is present the day will be imputed as 15. If the year is missing, the date will be considered missing. If this leads to contradictions for the start or end date of a concomitant therapy (e.g. imputed end date before documented start date) a partial end date will be imputed as the end of the interval or a partial start date will be imputed as the start of the interval in the database to resolve this contradiction.

If date and time information as well as a flag is missing for start of concomitant therapy, then the concomitant therapy is considered on-going at screening.

If date and time information as well as a flag is missing for end of concomitant therapy, then the concomitant therapy is considered on-going at end of study.

[REDACTED]

[REDACTED]

